4. Women of childbearing potential (WOCBP) must agree to abstain from sexual intercourse or to use 2 highly effective ([Appendix 7](#)) forms of contraception, at least one of which must be a barrier method, from the time of giving informed consent throughout the study, and for 5 months after the last dose of study treatment. Ivosidenib, nivolumab, and ipilimumab may have adverse effects on a fetus in utero. Furthermore, it is not known if nivolumab and ipilimumab have transient adverse effects on the composition of sperm. Subjects should be informed that taking the study medication may involve unknown risks to the fetus (unborn baby) if pregnancy were to occur during the study. Egg donation (ova, oocytes), for the purpose of reproduction, will not be allowed during the study and for 3 months after the last dose of study treatment.

- Male subjects with WOCBP partners must use a condom during the study and until at least 3 months after the last dose of study treatment. In addition, contraception should be considered for their female partners. Contraceptive measures do not apply if the subject is sterile, vasectomized, or sexually

abstinent. Sperm donation from male subjects will not be allowed during the study and for 3 months after the last dose of study treatment.

Please refer to [Appendix 7](#) for further contraception considerations.

Informed Consent

5. Obtained prior to any study-specific procedure as described in Section [13.3](#) of the protocol.

Medical and Therapeutic Criteria

6. Have a histopathological diagnosis consistent with nonresectable or metastatic cholangiocarcinoma and are not eligible for curative resection, transplantation or ablative therapies.
7. Have documented IDH1 gene-mutated disease based on local testing procedure (R132C/L/G/H/S mutations variants tested). Preferably using a tumor biopsy sample collected within the last 3 years.
- 8a. Have disease progression or treatment intolerance following at least 1 and no more than 2 prior systemic regimens for advanced disease (nonresectable or metastatic) including the following:
 - i. For Cohort 1: subjects who have not received any prior immune checkpoint inhibitor therapy but received at least 1 gemcitabine- or 5-FU-containing regimen for advanced cholangiocarcinoma.

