5. STUDY POPULATION AND WITHDRAWAL OF PARTICIPANTS

5.1. Inclusion Criteria

Participants are eligible to be enrolled in the study only if all the all the following criteria apply:

Demographic Characteristics

1. Male or female participant age \geq 18 years old.

General Criteria

2. Estimated life expectancy \geq 12 weeks.
3. ECOG performance status \leq 1.

Sex and Contraceptive/Barrier Requirements

4. Women of childbearing potential (WOCBP) must agree to abstain from sexual intercourse or to use 2 highly effective ([Appendix 7](#)) forms of contraception, at least one of which must be a barrier method, from the time of giving informed consent throughout the study, and for 5 months after the last dose of study treatment. Ivosidenib, nivolumab, and ipilimumab may have adverse effects on a fetus in utero. Furthermore, it is not known if nivolumab and ipilimumab have transient adverse effects on the composition of sperm. Subjects should be informed that taking the study medication may involve unknown risks to the fetus (unborn baby) if pregnancy were to occur during the study. Egg donation (ova, oocytes), for the purpose of reproduction, will not be allowed during the study and for 5 months after the last dose of study treatment.
- Male subjects with WOCBP partners must use a condom during the study and until at least 3 months after the last dose of study treatment. In addition, contraception should be considered for their female partners. Contraceptive measures do not apply if the subject is sterile, vasectomized, or sexually abstinent. Sperm donation from male subjects will not be allowed during the study and for 3 months after the last dose of study treatment.

Note: Please refer to [Appendix 7](#) for further contraception considerations.

Informed Consent

5. Obtained prior to any study-specific procedure as described in Section 13.3 of the protocol.

Medical and Therapeutic Criteria

6. Have a histopathological diagnosis consistent with nonresectable or metastatic cholangiocarcinoma and are not eligible for curative resection, transplantation or ablative therapies.
7. Have documented IDH1 gene-mutated disease based on local testing procedure (R132C/L/G/H/S mutations variants tested). Preferably using a tumor biopsy sample collected within the last 3 years.
- 8a. Have disease progression or treatment intolerance following at least 1 and no more than 2 prior systemic regimens for advanced disease (nonresectable or metastatic) including the following:

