Appendix 13: Local modification of the clinical study protocol (GBR)

FINAL VERSION DATE:	20 December 2023
COUNTRY CONCERNED:	United Kingdom
CENTRES CONCERNED:	All centres in United Kingdom
NATURE OF MODIFICATIONS	

- Update of inclusion criteria 4 and Appendix 7 to clarify acceptable contraception methods.- In line with CTFG guidance, an additional pregnancy test to be performed at the end of the relevant systemic exposure; at the 100-day safety follow up visit.- Clarification added to section 8.4 that all SAEs must be reported to the sponsor immediately and within 24 hours of awareness at the latest.	

Paragraph impacted 5.1 Inclusion Criterion- 4 - Sex and Contraceptive/Barrier requirements
Amended text:

Women of childbearing potential (WOCBP) must agree to abstain from sexual intercourse or to use 2 forms of contraception, one of which must be highly effective and one a barrier method (Appendix 7) highly effective (Appendix 7) forms of contraception, at least one of which must be a barrier method, from the time of giving informed consent throughout the study, and for 5 months after the last dose of study treatment.

Paragraph impacted Appendix 7 - Contraception considerations
Amended text:

Definition of acceptable contraception methods for the study: ~~Acceptable contraception methods for the study are those considered as highly effective methods~~, In addition to a highly effective method, the second form of contraception may include male or female condom with or without spermicide, cap, diaphragm or sponge with spermicide.

Paragraph impacted 4.1.2 Investigational Schedule

Amended text: a new cross (X) is present in the Table (4.1.2) 1 column safety follow-up 100 (+5) Days After Last Nivolumab Dose and line pregnancy test.

Table (19) 1 - Schedule of Assessments for Subjects in the Safety Lead-in Phase and Expansion Phase

Visit/Cycle	Screening ¹	Cycle 1 (21 Days)			Cycle 2 (21 Days)		Cycles 3 and 4 (21 Days)	Cycle 5 and Beyond (28 Days Each Cycle)	End of Treatment ²	Safety Follow-up ²		PFS Follow-up ³	Survival Follow-up
Study Day	D-28 to D-1	D1	D8	D15 (± 2 Days)	D1 (± 2 Days)	D15 (± 2 Days)	D1 (± 2 Days)	D1 (± 2 Days)	Within 7 Days After Last Dose	30 (+5) Days After Last Dose	100 (+5) Days After Last Nivolumab Dose		Every 12 weeks (± 2 weeks)
Allocation to IMP ⁴		X			X		X	X					
Informed Consent	X												
Inclusion/Exclusion Criteria	X												
Demographics	X												
Disease History	X												

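### Inclusion criterion 4 bans egg donation for 3 months after the last dose in the synopsis but for 5 months in Section 5.1

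*Protocol*

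**What the plan says.** The protocol synopsis, under inclusion criterion 4, states: "Egg donation (ova, oocytes), for the purpose of reproduction, will not be allowed during the study and for 3 months after the last dose". Section 5.1, under the same criterion number, states: "Egg donation (ova, oocytes), for the purpose of reproduction, will not be allowed during the study and for 5 months after the last dose". Population, activity and starting point are the same in both; only the number of months differs.

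The rest of the criterion agrees. In both places women of childbearing potential must use contraception "from the time of giving informed consent throughout the study, and for 5 months after the last dose of study treatment". Men with partners of childbearing potential must use a condom until at least 3 months after the last dose. For sperm, both places say: "Sperm donation from male subjects will not be allowed during the study and for 3 months after the last dose of study treatment".

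**The concern.** The criterion sets a restriction that binds participants after treatment ends, and the current protocol gives it two lengths. The synopsis list is not offered as background: its lead-in requires subjects to meet all of the criteria that follow. Between months 3 and 5 after the last dose the two statements give opposite answers to the question of whether donation is allowed.

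What is at stake is a clear instruction on reproductive safety. Criterion 4 itself warns that all three drugs may harm a fetus. Section 13.3 requires the investigator to explain the study's requirements to each participant, and Section 14.2 permits no deviations. A site asked about month 4 cannot give one answer that fits both statements.

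**Working it through.** No sample size, power or error rate is involved, so the check is a side-by-side reading followed by a search for any text that resolves the difference.

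**Periods after the last dose in criterion 4**

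| Item | Synopsis | Section 5.1 |
|---|---|---|
| Contraception, women of childbearing potential | 5 months | 5 months |
| Egg donation | 3 months | 5 months |
| Condom use, men | 3 months | 3 months |
| Sperm donation | 3 months | 3 months |

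One of the four periods differs, by 5 − 3 = 2 months. The mismatch is therefore confined to this item and does not run through the whole criterion.

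**Places that might have resolved it**

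- Protocol Appendix 7 defines childbearing potential and contraceptive methods. It gives no period after treatment.
- Protocol Appendix 13, the UK modification, describes its change as: "Update of inclusion criteria 4 and Appendix 7 to clarify acceptable contraception methods". The amended text shown repeats the 5-month contraception period and contains no sentence on egg donation.
- The amendment-log entries available for review (versions 3.0 to 5.0) do not mention egg donation.

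**Is it an artefact of the document?** Neither statement is redacted, neither comes from the amendment log, and both figures stand in plain sentences, not in a table that could have been broken in reading.

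**Where the disputed months fall.** Section 8.10.1 collects pregnancies for up to 180 days after the last administration, or until new anti-cancer therapy if earlier. At the SAP's conversion of 30.4375 days per month, 3 months is 3 × 30.4375 = 91.3 days and 5 months is 5 × 30.4375 = 152.2 days. Both lie inside 180 days, so the disputed interval falls in a period that the protocol still treats as relevant to reproductive safety, unless new therapy has begun.

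**The case against.** The case on the other side concerns consequence, because the mismatch itself is plain. Four parts of it stand.

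- **The study has ended early.** SAP Section 1 records that enrollment stopped in the Safety Lead-in phase and that a termination letter was issued on 21 August 2024. SAP Section 5 gives 7 patients enrolled. Nobody further is due to be screened under criterion 4, and nothing in the documents points to another amendment.
- **Sites are directed to Section 5.1.** Section 9.1 names it as the list to review and document. This bears on which page sites work from, not on which period is right.
- **The contraception period is consistent.** It is 5 months in both places, so the protection against pregnancy in participants does not conflict.
- **Exposure is remote.** Participants have previously treated nonresectable or metastatic cholangiocarcinoma, for which Section 2.1.2 puts survival on second-line chemotherapy at approximately 6 months. Egg donation 3 to 5 months after the last dose is unlikely.

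Two stronger readings are tempting. A reader might infer that what a woman was told depended on which page her site copied. The documents do not support that: Sections 13.1, 13.3 and 13.4 have participants informed through a separate consent form that goes to the ethics committee, and that form was not available here. A reader might also infer that the synopsis contradicts itself by lifting the donation ban while contraception is still required. Different periods for different activities are not in themselves a contradiction, and criterion 4 states no risk specific to donated eggs. The contradiction lies only between the synopsis and Section 5.1.

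Early termination does not remove the point entirely. The restriction runs from the last dose, and Section 4.3.1 allows subjects who are benefiting to stay on study drug if the study is discontinued for reasons other than safety. A restriction period could therefore begin after the termination letter. The documents do not give the reason for termination.

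**Conclusion.** The inconsistency is real and minor. Current protocol text gives 3 months and 5 months for the same restriction, and nothing in the documents reviewed resolves it. It touches no endpoint, estimand, analysis set, toxicity rule or sample size.

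Its reach is bounded by the 7 enrolled patients. How many of them were women of childbearing potential is not stated, so the number affected is unknown and may be zero. The documents do not show which period participants were told, so no harm and no misinformation can be claimed. The conclusion assumes only that both statements are in force in version 5.0, as their place in the text indicates.

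**What to change.** Reconcile the synopsis and Section 5.1 so that criterion 4 carries one egg-donation period. The sponsor must decide which period that is; this review does not. If the protocol is amended again for any reason, the cost is one number.

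If no amendment is planned, a short clarification would serve. It should go to sites with any woman of childbearing potential still on treatment or in follow-up, and should ask them to check that the consent form states the same period. If there is no such woman, it is enough to record the discrepancy in the study file.

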Appendix 5: End of Cohort Meeting Minutes Template End of cohort meeting minutes	124
Appendix 6: Instructions to Investigator for Handling Data Rights Requests.....	125
Appendix 7: Contraception Considerations	127
Appendix 8: Adverse Event Criteria for Delay, Resume, and Discontinue of Nivolumab and Ipilimumab	128
Appendix 9: Management Algorithms for Studies Under CTCAE Version 5.0	133
Appendix 10: ECOG Performance Status and Prohibited Concomitant Medications	142
Appendix 11: Examples of Low-Fat and High-Fat, High-Calorie Meals	144
Appendix 12: National Cancer Institute Common Terminology Criteria for Adverse Events	145
Appendix 13: Local modification of the clinical study protocol (GBR).....	147

List of abbreviations

Abbreviation	Definition
2-HG	Plasma 2-hydroxygluturate
5-FU	5-fluorouracil based chemotherapy
ADA	Anti-Drug Antibody
ADL	Activities of daily living
AE	Adverse Events
AESI	Adverse events of special interest
ALT	Alanine aminotransferase
AML	Acute Myeloid Leukemia
AST	Aspartate aminotransferase
AUC	Area under the concentration
AUC _{0-∞}	Area under the concentration from 0 to infinity
AUC _{0-t}	0 to time of last measurable concentration
AUC _{tau,ss}	Area under the concentration over 1 dosing interval at steady state
BOR	Best overall response
BTC	Biliary tract cancer
C1D1	Cycle 1 Day 1
CCA	Cholangiocarcinoma
CD	Combination Dose
cHL	classical Hodgkin Lymphoma
CI	Confidence Interval
CL	Clearance
CL/F	Apparent Clearance
C _{max}	Maximum Concentration
CR	Confirmed complete response
CRC	Colorectal Cancer
CRO	Contract research organizations
CSR	Clinical study report
CT	Cytotoxic T
ctDNA	Circulating tumor DNA
CTLA4	Cytotoxic T-lymphocyte associated protein 4
C _{trough}	Trough concentration
CV	Curriculum vitae
CYP	Cytochrome p450
DCR	Disease control rate
DLT	Dose limiting toxicities
DOR	Duration of response
DRT	Data review team
ECG	Electrocardiogram
ECOG	Eastern cooperative oncology group
eCRF	Electronic case report form
EDC	Electronic data capture
EEA	European economic area
EOT	End of Treatment
EU	European union

FDA	Food and drug administration
FDG	Fluorodeoxyglucose
FGFR	Fibroblast growth factor receptor
FSP	Full service provider
GCP	Good clinical practice
GLP	Good laboratory practice
HCC	Hepatocellular Carcinoma
HPBL	Human peripheral blood lymphocyte
HR	Hazard ratio
IB	Investigator brochure
iCCA	Intrahepatic
ICF	Informed consent form
ICI	Immune checkpoint inhibitors
IDH1	Isocitrate dehydrogenase 1
IE	Intercurrent events
IEC	Independent ethics committee
Ig	Immunoglobulin
IMAE	Immune-mediated adverse events
IMP	Investigational medicinal product
INR	International normalization ratio
IO	Immuno-oncology
irAE	Immune-related adverse events
IRB	Institutional review board
IV	Ivosidenib
LEVF	Left ventricular ejection fraction
mAb	Monoclonal antibody
MedDRA	Medical dictionary for regulatory activities
MRI	Magnetic resonance imaging
MUGA	Multiple gated acquisition
NE	Not evaluable
NSCLC	Non-small cell lung cancer
ORR	Objective response rate
OS	Overall survival
PBMC	Peripheral blood mononuclear cells
PD	Pharmacodynamic
PD-L1	Programmed death-ligand 1
PD-L	Programmed death 1
PET	Positron emission tomography
PFS	Progression-free survival
PK	Pharmacokinetics
PR	Partial response
PRES	Posterior reversible encephalopathy syndrome
PT	Prothrombin time
Q2W	Once every 2 weeks
Q3W	Once every 3 weeks
Q4W	Once every 4 weeks
QD	Once daily
QTcF	QT interval using Fridericia's formula

R/R	Relapsed or refractory
RCC	Renal cell carcinoma
RCD	Recommended combination Dose
RECIST	Response evaluation criteria in solid tumors
RTSM	Randomization and trial supply management
SAP	Statistical analysis plan
SAE	Serious adverse events
SCCHN	Squamous cell carcinoma of head and neck
SCLC	Small cell lung cancer
SD	Stable disease
SmPC	Summary of product characteristics
T _{1/2}	Time required for drug concentration
TEAE	Treatment-emergent adverse events
T _{max}	Time to maximum concentration
TTR	Time to response
ULN	Upper limit of normal
US	United States
USPI	US prescribing information
Vd/F	Apparent volume of distribution
WMA	World medical association
WOCBP	Women of childbearing potential
WT	Wild-type tumors

1. ADMINISTRATIVE STRUCTURE OF THE STUDY

Non-Sponsor parties, Sponsor parties, and contract research organizations (CROs) responsible for local management of the study are described in a separate document entitled “Administrative Part of Clinical Study Protocol.” The list of Investigators is given in a separate document attached to the protocol and entitled “Investigators.”

2. BACKGROUND INFORMATION

2.1. Cholangiocarcinoma

2.1.1. Overview of Cholangiocarcinoma

Cholangiocarcinomas (CCAs) are rare cancers (accounting for 3% of all gastrointestinal malignancies) that arise from biliary epithelium and are typically diagnosed at advanced stages for which curative surgery is not feasible. The classification of CCAs is divided anatomically as extrahepatic, intrahepatic (iCCA), and perihilar ([Saha et al, 2014](#); [Van Dyke et al, 2019](#)). The disease is often advanced and incurable at the time of diagnosis. Common presentation includes symptoms related to biliary tract obstruction including jaundice, abdominal pain, weight loss, fever, fatigue, and abnormal liver function tests. The prognosis for subjects with CCA is poor; regardless of stage at diagnosis, the 5-year survival rates associated with both intrahepatic (iCCA) and extrahepatic CCA are 9% to 10% and only 2% in subjects with distant metastases ([ACS, 2021](#)). CCA (intrahepatic and extrahepatic) affects approximately 8,000 people in the US annually ([ACS, 2019](#)) and approximately 1.3 in 10,000 people in the EU ([Agency, 2018](#)).

Isocitrate dehydrogenase-1 (IDH1) mutations occur globally in approximately 16%, and up to 29% in some reports, of iCCAs and approximately 0% to 7% of extrahepatic CCAs. Using a maximum incidence of 14% (13% for intrahepatic + 1% for extrahepatic) for IDH1 mutations in CCA indicates an overall prevalence of 0.182 in 10,000 people ([Kendre et al, 2022](#)). Based on majority of available literature, IDH1 mutations do not have a prognostic impact on clinical outcomes including progression-free survival (PFS) and overall survival (OS) ([Boscoe et al, 2019](#)). Therefore, outcomes in this biomarker-selected population can be compared to those reported among the general advanced, previously treated CCA population ([Boscoe et al, 2019](#); [Goyal et al, 2015](#)).

2.1.2. Current Treatment of Cholangiocarcinoma

As early-stage disease is commonly asymptomatic, only a minority of CCA subjects are diagnosed with resectable disease, while most of the subjects present with locally nonresectable or metastatic disease ([Rizzo et al, 2021](#)). The first-line standard of care treatment for subjects with CCA, including subjects with IDH1 mutation-positive CCA, in a locally nonresectable or metastatic setting is a combination of durvalumab with gemcitabine/cisplatin and a combination of pembrolizumab with gemcitabine/cisplatin. Approval of durvalumab in combination with gemcitabine/cisplatin was granted starting in 2022 in the US, EU, UK and other parts of the world and was based on the Phase 3 TOPAZ-1 trial evaluating the durvalumab and gemcitabine/cisplatin combination *vs.* gemcitabine/cisplatin. The addition of durvalumab resulted in an improved OS of 12.8 months compared with a gemcitabine/cisplatin OS of 11.5 months (hazard ratio [HR]: 0.80, confidence interval [CI]: 0.66-0.97, $p = 0.021$) ([Oh et al, 2022](#)). Approval of pembrolizumab in combination with gemcitabine/cisplatin was granted in

2023 in the US and was based on the Phase 3 Keynote-966 trial evaluating pembrolizumab and gemcitabine/cisplatin combination vs. gemcitabine/cisplatin. The addition of pembrolizumab resulted in an improved OS of 12.7 months compared to a gemcitabine/cisplatin OS of 10.9 months (HR: 0.83, CI: 0.72–0.95, $p = 0.0034$) (Kelley *et al*, 2023).

Second-line chemotherapy regimens produce an incrementally smaller therapeutic benefit, with an average median PFS of 2 to 3 months (Brieau *et al*, 2015; Lamarca *et al*, 2021). Overall survival outcomes are also limited to approximately 6 months (Kim *et al*, 2017; Lamarca *et al*, 2021; Matsuyama *et al*, 2018; Ying and Chen, 2019), demonstrating the need for novel treatment options in subjects with CCA.

Recent years have seen the advent of novel treatments in the biliary tract cancer (BTC) landscape, including targeted therapies (ivosidenib, pemigatinib, infigratinib, and futibatinib) and immune checkpoint inhibitors (ICIs), as monotherapy or in combination (Rizzo *et al*, 2021).

Ivosidenib, a potent and selective inhibitor of the IDH1 mutant protein, is the only drug approved for the treatment of adult subjects with previously treated, locally nonresectable or metastatic CCA with an IDH1 mutation (approval granted in the US in 2021). Pemigatinib, infigratinib, and futibatinib, selective inhibitors of fibroblast growth factor receptor (FGFR), are approved for treatment of adult subjects with previously treated, locally nonresectable or metastatic CCA who have *FGFR2* fusions or rearrangements (approved in the US in 2020, 2021, and 2022, respectively). Pemigatinib is also approved in EU (approval granted in 2021). FGFR fusions are detected in 10% to 15% of subjects with iCCA (Saborowski *et al*, 2020), however they rarely co-occur (less than 1% of subjects) with mutations of IDH1 (Abou-Alfa *et al*, 2020).

The activity of ICIs (programmed death-1 [PD-1], programmed death-ligand 1 [PD-L1]) in previously treated BTC has been tested with heterogeneous results. Results with ICI monotherapy in unselected BTCs, including CCA, suggest limited activity in recurrent disease; the objective response rate (ORR) of single-agent anti-PD-1 is approximately 10% (Doki *et al*, 2022; Kim *et al*, 2020; Klein *et al*, 2020; Piha-Paul *et al*, 2020).

Two Phase 1/2 studies testing the combination of a PD-1 or PD-L1 inhibitor with an anti-cytotoxic T-lymphocyte associated protein 4 (CTLA4) agent showed superior efficacy than any compound alone. Durvalumab (anti-PD-L1) in combination with tremelimumab (anti-CTLA4) was tested in Asian subjects resulting in an ORR of 10.8% and a median OS of 10.1 months (Doki *et al*, 2022). In the second trial, nivolumab (anti-PD-1) plus ipilimumab (anti-CTLA4) (Klein *et al*, 2020) was administrated to 39 Australian subjects (16 with iCCA) resulting in an ORR of 23% (31% iCCA), and median PFS and median OS of 2.9 and 5.7 months, respectively. These preliminary results appear to suggest that combination of anti-PD-1 with anti-CTLA4 has superior efficacy compared with anti-PD-1 monotherapy and warrants further investigation in larger clinical trials.

